3 STUDY DESIGN

3.1 GENERAL DESCRIPTION

This is a Phase 4, prospective, open label, single arm, interventional study, to be conducted in the US, to evaluate the safety and tolerability of Fabrazyme at approved dose of 1 mg/kg and increased infusion rate and reduced infusion volume.

Up to 14 participants with Fabry disease will be enrolled to study intervention in 4 cohorts:

- Cohort 1: 3 Fabrazyme experienced female participants (body weight ≥30 kg)
- Cohort 2: 3 Fabrazyme experienced non-classic male participants (body weight ≥30 kg)
- Cohort 3: 4 Fabrazyme experienced classic male participants (body weight ≥30 kg)
- Cohort 4: 4 Fabrazyme experienced participants (body weight <30 kg)

Classic FD is defined by α GAL level in dried blood spot or leukocyte below 3% of normal value and all others are considered as non-classic disease.

Screening will be performed up to 4 weeks prior to the first dose of study intervention. Enrolled participants will receive treatment for up to 16 weeks and have an End-of-Study Visit 28 weeks after the start of the treatment. Participants will undergo visits and study procedures as shown in Schedule of Activities (SoA) presented in Section 1.3 of the protocol. A flow chat illustrating the key components of the study is provided in Figure 1.

Document: \\ieedc-

 $vnasc01\BIOS data\Sanofi\Fabrazyme\IAB16602\Biostatistics\Documentation\SAP\SAP\Sanofi\Final$

Version\lps17726-16-1-9-sap.docx

Author: Version Number: Final V1.0

Version Date: 22Oct2024

[figure not shown]
Template No.: CS_TP_BS016 Revision 7 Reference: CS_WI_BS005

Effective Date: 01Nov2021

Page 18 of 65

Figure 1: Study Schema

Abbreviations: ADA = anti-drug antibody (ie, anti-agalsidase beta IgG antibody); AE = adverse event; AESI = adverse event of special interest; EOS = end-of-study; EOT = end-of-treatment; IAR = infusion associated reaction; lyso-GL3 = globotriaosylsphingosine; Q2W = every 2 weeks; SAE = serious adverse events; V = visit; W = week.

- a. V1 and V2 can take place on the same day. The number of visits during the Study Intervention Period (ie, Visits 2 to 10) may differ between participants, as those having a second IARs will discontinue the study intervention, and those who successfully reaches the shortest infusion duration planned for the cohort to which they belong will be considered as treatment completers. All participants will stay in the study for the follow-up visits at Week 12 and Week 28.
- b. IARs will be collected only during the Study Intervention Period which can be shorter than 16 weeks for some participants.

Document: \\ieedc-

Author:

vnasc01\BIOSdata\Sanofi\Fabrazyme\IAB16602\Biostatistics\Documentation\SAP\SAP\Sanofi\Final

Version\lps17726-16-1-9-sap.docx

Version Number: Final V1.0

Version Date: 22Oct2024

Template No.: CS_TP_BS016 Revision 7 Reference: CS_WI_BS005

Effective Date: 01Nov2021

PROTOCOL LPS17726

Analysis Plan Template

Page 19 of 65

3.1.1 Infusion Duration Guideline

All participants will receive Fabrazyme infusions at dose of 1 mg/kg of body weight every 2 weeks at the study site, for up to 16 weeks. The infusion duration will shorten, and the infusion rate will rise with each successfully tolerated infusion, until they reach the minimum infusion duration of 20 minutes for participants in cohorts 1 to 3 (≥30 kg) and 30 minutes for participants in cohort 4 (<30 kg). When the participant successfully reaches the shortest infusion duration planned for the cohort which he/she belongs to, he/she will be considered a treatment completer and will not receive any further infusion as part of the study, regardless of whether the treatment period reaches 16 weeks or not.

Infusion duration tolerated by a participant is an infusion at which they successfully receive an infusion within an actual duration not exceeding 120% of planned duration without an IAR. If the participant receives several infusions at the same planned duration during the treatment period, the infusion duration will be considered tolerated if the last infusion received is without IAR and does not exceed 120% of planned duration.

The decrease in the infusion duration for participants in cohorts 1 to 3 (with \geq 30 kg body weight) will follow the flow diagram presented in Figure 2. The decrease in the infusion duration for participants in cohort 4 (with \leq 30 kg body weight) will follow the flow diagram presented in Figure 3.

Document: \\ieedc

 $vnasc01\BIOS data\Sanofi\Fabrazyme\IAB16602\Biostatistics\Documentation\SAP\SAP\Sanofi\Final$

Version\lps17726-16-1-9-sap.docx

Author: Version Number: Final V1.0

Version Date: 22Oct2024

[figure not shown]
Template No.: CS_TP_BS016 Revision 7 Reference: CS_WI_BS005

Effective Date: 01Nov2021

Page 20 of 65

Figure 2: Guideline for Decreasing Infusion Duration for Participants ≥30 kg

Abbreviations: IAR = infusion associated reaction.

Note: IARs occurring during a single infusion are counted as one IAR. Only when an IAR occurs in relation to a separate infusion it will be considered as a second IAR.

Note: When a second IAR occurs, the participant will discontinue study intervention and the previous highest rate tolerated by the participant will be considered as the maximum tolerated rate for this participant.

Document: \\ieedc

Author:

vnasc01\BIOSdata\Sanofi\Fabrazyme\IAB16602\Biostatistics\Documentation\SAP\SAP\Sanofi\Final

Version\lps17726-16-1-9-sap.docx

Version Number: Final V1.0

Version Date: 22Oct2024

[figure not shown]
Template No.: CS_TP_BS016 Revision 7 Reference: CS_WI_BS005

Effective Date: 01Nov2021

Page 21 of 65

Figure 3: Guideline for Decreasing Infusion Duration for Participants <30 kg

Abbreviations: IAR = infusion associated reaction.

Note: IARs occurring during a single infusion are counted as one IAR. Only when an IAR occurs in relation to a separate infusion it will be considered as a second IAR.

Note: When a second IAR occurs, the participant will discontinue study intervention and the previous highest rate tolerated by the participant will be considered as the maximum tolerated rate for this participant.

Document: \\ieedc

vnasc01\BIOSdata\Sanofi\Fabrazyme\IAB16602\Biostatistics\Documentation\SAP\SAP\Sanofi\Final

Version\lps17726-16-1-9-sap.docx

Author: Version Number: Final V1.0

Version Date: 22Oct2024

Template No.: CS_TP_BS016 Revision 7 Reference: CS_WI_BS005

Effective Date: 01Nov2021

Page 22 of 65

3.2 SCHEDULE OF EVENTS

Schedule of events can be found in Section 1.3 of the protocol.

3.3 CHANGES TO ANALYSIS FROM PROTOCOL

The following presents the updated changes to analysis from protocol section 9.0, version 2.0 (Protocol Amendment Number 1.0), dated 20May2024.

Table B - Changes to Analysis from Protocol

Analysis in SAP	
Reason for Update: ADA analysis will include summaries of ADA attributes, titer, incidence, and kinetics of ADA response. Also, "6 months follow-up" will include "each visit where plasma lyso-GL3 (ng/mL)/ADA titer is recorded" to make it clear that all post-baseline visits will be considered for analysis as per the windowing convention described in Section 6.6 'Windowing Conventions'. Refer to Section 15.3.1 for the full descriptions of derivations and analyses.	
Reason for Update: Analyses with limited value are removed: The 95% confidence intervals will not be presented due to the small sample size. Shift tables will not be presented. Change from baseline will only be derived for continuous measurements of select variables specified in the SAP. See Section 7: 'Statistical Considerations'	

Document: \\ieedc-

vnasc01\BIOSdata\Sanofi\Fabrazyme\IAB16602\Biostatistics\Documentation\SAP\SAP\Sanofi\Final

[figure not shown]
Version\lps17726-16-1-9-sap.docx

Author: Version Number: Final V1.0

Version Date: 22Oct2024

Template No.: CS_TP_BS016 Revision 7 Reference: CS_WI_BS005

Effective Date: 01Nov2021

Page 23 of 65

Analysis in Protocol	Analysis in SAP
Categorical data will be summarized using count and percentage (the percentage of participants in each category relative to the total number of participants in the relevant analysis set or relative to the total number of participants in the relevant analysis set, with assessments available [where appropriate]) in each category. A 95% CI will be provided for the binary endpoint as appropriate. The change from baseline in distribution for the categorical endpoint_will be presented with a shift table; number and percentage of participants will be provided.	
Analysis of Cohorts ■ The data will be summarized per cohort and by pooled cohorts as described in Sections 9.3.2, 9.3.3 and 9.3.4, and where appropriate, per infusion duration.	Reason for Update: Data will be summarized by pooled cohorts 1-4 only. This is because there are very few participants within each cohort. See Section 7: 'Statistical Considerations'

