	Treatment : Fabrazyme 1 mg/kg Q2W up to the rate tolerated (refer to Section 6.2), with oral premedications given 30 minutes prior to each infusion.
	Endpoint : Binary, calculated separately for each infusion duration: Participant achieved infusion duration without experiencing any IAR.
	Intercurrent events: A while-on-treatment approach will be applied. Participants never observed to tolerate any infusion rate will be counted as not achieving the required duration for the infusion. A treatment policy approach will be applied in case pre-medications are not given as described within the protocol. No action will be taken for this event for the analysis even when pre-medications are not given as described within the protocol.
	Summary measure : For each infusion duration, number and % of participants achieving the endpoint.

Objectives	Estimand Description/Endpoints	
	Population : Participants with confirmed diagnosis of FD, age 2 to 65 years, Fabrazyme-experienced, treated for at least 3 months without IARs during the most recent 3 infusions.	
	Treatment : Fabrazyme 1 mg/kg Q2W up to the rate tolerated (refer to Section 6.2), with oral premedications given 30 minutes prior to each infusion.	
	Endpoint : Binary, calculated separately for each infusion duration: Participant achieved infusion duration without experiencing a second IAR.	
	Intercurrent events: A while-on-treatment approach will be applied. Participants never observed to tolerate any infusion rate will be counted as not achieving the required duration for the infusion. A treatment policy approach will be applied in case pre-medications are not given as described within the protocol. No action will be taken for this event for the analysis even when pre-medications are not given as described within the protocol.	
	Summary measure: For each infusion duration, number and % of participants achieving the endpoint.	
Exploratory		
To investigate the influence of increased infusion rate on the immunogenicity and efficacy of	Changes of plasma lyso-GL3 from baseline to 6 months follow-up	
Fabrazyme treatment	Change of the titer of ADA to Fabrazyme over 6 months follow-up	
Safety		
To investigate the influence of increased infusion rate on the safety of Fabrazyme treatment	Number, severity, and nature of AEs including IARs	

Abbreviations: ADA = anti-drug antibody, AE = adverse event; FD = Fabry disease; IAR = infusion associated reaction; lyso-GL3 = globotriaosylsphingosine; Q2W = every 2 weeks.

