4.2 Scientific Rationale for Study Design

A single arm design was selected as the main objective is to evaluate the safety and tolerability of increases in Fabrazyme infusion rate, and within a participant, the longer-lasting infusions might be used as the comparators for the shorter ones. An open label design was selected as all participants will receive the same intervention and the duration of the infusion decreases as the study progresses, which is automatically recognizable to the participants and study personnel.

The population chosen for the study comprises the diversity of patients with FD already treated with Fabrazyme: women, men with classic and non-classic disease, and children.

Standard clinical and laboratory procedures will be utilized in this study. All efficacy and safety-related measurements in this study are standard for participants with FD. All clinical and laboratory procedures in this study are standard and generally accepted.

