9.3 Statistical Analyses

9.3.1 General Considerations

All analyses, summaries, and listings will be performed using SAS® software (version 9.4 or higher) unless otherwise noted. All details regarding the statistical analysis and the preparation of tables, listings and figures will be described in the SAP.

The analysis of complete data for the study will be performed when all the participants have either completed the study or discontinued early from the study, all data from the study are in the database, and the database is locked.

In general, descriptive statistics of efficacy and safety parameters (result and change from baseline) by scheduled visits will be provided on observed cases, ie, inclusion of only participants having non-missing assessments at a specific visit. The data will be summarized per cohort and by pooled cohorts as described in Sections 9.3.2, 9.3.3 and 9.3.4, and where appropriate, per infusion duration.

The observation period of safety data will be as follows:

• Pre-treatment period: The pre-treatment observation period is defined from the signed informed consent up to the first dose of study intervention.

• Treatment Emergent (TE) period: The TE period is defined as the time from the first dose of study intervention to the last dose of study intervention + follow-up period.

The following descriptive statistics will be used as applicable to summarize the study data unless otherwise specified:

- Continuous data will be summarized using the number of observations available (n, mean, standard deviation [SD], minimum, median, 1st quartile, 3rd quartile, and maximum).
 Additionally, for the absolute change or percent change from baseline analysis, a 95% confidence interval (CI) will be provided.
- Categorical data will be summarized using count and percentage (the percentage of
 participants in each category relative to the total number of participants in the relevant
 analysis set or relative to the total number of participants in the relevant analysis set, with
 assessments available [where appropriate]) in each category. A 95% CI will be provided
 for the binary endpoint as appropriate. The change from baseline in distribution for the
 categorical endpoint will be presented with a shift table; number and percentage of
 participants will be provided.

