15 ENDPOINT EVALUATION

15.1 PRIMARY ENDPOINTS

15.1.1 PRIMARY ENDPOINT VARIABLE(S)

15.1.1.1 SHORTEST INFUSION DURATION EACH PARTICIPANT TOLERATES

The shortest infusion duration tolerated is the actual shortest duration (highest infusion rate) of a completed infusion tolerated by the participant without experiencing a second IAR.

A completed infusion is an infusion during which the entire amount of the study drug planned to be given at the visit has been delivered to the participant via infusion and the question "Was the infusion adjusted from the planned infusion?" is answered either "Infusion not changed" or "Infusion interrupted" on the Fabrazyme eCRF page. If the infusion was interrupted, it will only be considered completed if it was restarted, ie, the stop time of study drug infusion is later than the stop time of infusion interrupted.

An infusion is considered tolerated if it is completed within an actual duration (excluding any interruptions) not exceeding 120% of planned duration, without IAR. If the participant receives several infusions at the same planned duration during the study treatment period, the infusion duration will be considered tolerated if the last infusion with the duration is tolerated. Data for infusion duration tolerated at each visit (scheduled and unscheduled) is captured on the Fabrazyme eCRF pages.

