- Whether the participant tolerated the planned infusion duration without experiencing a second IAR (yes/no), calculated separately per each planned infusion duration.

Document: \\ieedc-

vnasc01\BIOSdata\Sanofi\Fabrazyme\IAB16602\Biostatistics\Documentation\SAP\SAP\Sanofi\Final

Version\lps17726-16-1-9-sap.docx

Author: Version Number: Final V1.0

Version Date: 22Oct2024

Template No.: CS_TP_BS016 Revision 7 Reference: CS_WI_BS005

Effective Date: 01Nov2021

PROTOCOL LPS17726

Analysis Plan Template

Page 47 of 65

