16.1.8 ANALYSIS OF ADVERSE EVENTS

Events with missing start/end dates and/or time will be handled according to the rules in Appendix 20.1 - 'Algorithm for Treatment Emergent Adverse Events'.

An overall summary table of all TEAEs will be provided for cohorts 1-4 pooled for the SAF

Document: \\ieedc

 $vnasc01\\BIOS data\\Sanofi\\Fabrazyme\\IAB16602\\Biostatistics\\Documentation\\SAP\\SAP\\Sanofi\\Finally and the properties of t$

[figure not shown]
Version\lps17726-16-1-9-sap.docx

Author: Version Number: Final V1.0

Version Date: 22Oct2024

Template No.: CS_TP_BS016 Revision 7 Reference: CS_WI_BS005

Effective Date: 01Nov2021

Page 55 of 65

analysis set and will provide the number and percentage of occurrences along with the total number of events for the following:

For all TEAEs:

- Participants with any TEAE
- Participants with any Severe TEAE
- Participants with any Treatment-Emergent SAE
- Participants with any TEAE leading to Death
- Participants with any TEAE leading to Permanent Discontinuation of Fabrazyme
- Participants with any Treatment-Emergent AESIs: IARs
- Participants with any Treatment-Emergent AESIs: Anaphylaxis
- Participants with any Treatment-Related TEAEs

The AE summaries provided on Table D will be generated with number and percentage of participants experiencing at least one event for the SAF analysis set. Additionally, AE listings in Table E will be provided by cohort for the SAF analysis set.

When evaluating the number of events for participants, multiple occurrences of the same event for the same participant (ie, same SOC and PT) will be as individual events in summary tables. Counts of all AE occurrences will be included in summary tables. All AE occurrences for each participant will be presented in listings.

Table D - Summary Analyses of adverse events

Type of AE	MedDRA levels	
All TEAEs	Primary System Organ Class and Preferred Term	
TEAEs by Maximal Intensity	Primary System Organ Class and Preferred Term	
TEAEs by Worst Relationship to Fabrazyme	Primary System Organ Class and Preferred Term	
Treatment Emergent SAEs	Primary System Organ Class and Preferred Term	
Treatment Emergent SAEs by Worst Relationship to Fabrazyme	Primary System Organ Class and Preferred Term	
TEAEs of Special Interest (IAR)	Primary System Organ Class and Preferred Term	

Document: \\ieedc-

 $vnasc01\\BIOS data\\Sanofi\\Fabrazyme\\IAB16602\\Biostatistics\\Documentation\\SAP\\SAP\\Sanofi\\Finally and the properties of t$

[figure not shown]

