16.4.5 ANALYSIS OF VITAL SIGNS AND WEIGHT

Vital signs data will be analyzed for the SAF analysis set for the following parameters:

- Systolic blood pressure (mmHg)
- Diastolic blood pressure (mmHg)
- Heart rate (bpm)
- Respiratory rate (bpm)
- Body temperature (°C)
- Weight (kg)

The following summaries based on observed data will be provided for the study treatment period:

- Values at each visit.
- Change from baseline at each visit for pre-dose vital signs.
- Change from pre-dose to post-dose at each visit (for all parameters except weight [kg])
- Incidence of predefined markedly abnormal criteria by age group and parameter.

Participants who have markedly abnormal values in both directions (abnormally high and abnormally low) during the study treatment period for the same parameter will be included in both high and low counts for that parameter.

Corresponding listings will also be provided detailing the above summaries, including the date and time of assessment and reasons if known as to why a scheduled assessment was not conducted. Listings will also include what abnormality is satisfied at each visit pre/post infusion.

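### The safety question is about infusion rate, but the SAP text has no safety summary by infusion duration, omits the protocol's exposure summary without saying so, and drops confidence intervals for a weak reason

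*SAP*

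**What the plan says.** - **Objective.** Protocol 3.0 (Table 2) gives the safety objective as "To investigate the influence of increased infusion rate on the safety of Fabrazyme treatment". Protocol 4.2 defends the single arm on the ground that "within a participant, the longer-lasting infusions might be used as the comparators for the shorter ones".
- **Grouping.** Protocol 9.3.1 has the data "summarized per cohort and by pooled cohorts as described in Sections 9.3.2, 9.3.3 and 9.3.4, and where appropriate, per infusion duration". SAP 3.3 (Table B) sets that line aside: "Data will be summarized by pooled cohorts 1-4 only. This is because there are very few participants within each cohort".
- **AEs and vital signs.** SAP 16.1.8: "An overall summary table of all TEAEs will be provided for cohorts 1-4 pooled for the SAF". The remaining AE tables are by system organ class and preferred term. SAP 16.4.5 summarises vital signs, including the change from before to after infusion, by visit.
- **What is kept by duration.** SAP 15.2.1.3 derives two participant-level indicators, one for no IAR at all and one for no second IAR. The second reads "Whether the participant tolerated the planned infusion duration without experiencing a second IAR (yes/no), calculated separately per each planned infusion duration". SAP 15.2.3 adds a stacked bar chart by cohort and planned duration, with IARs counted cumulatively, and a listing that flags responders on each secondary endpoint.
- **Exposure.** Protocol 9.3.5 commits to a descriptive summary of exposure duration and of the number of administrations. SAP 14 covers only dose-based compliance, and Table B does not mention exposure.
- **Intervals.** Protocol 9.3.1 provides 95% intervals for binary endpoints as appropriate. Table B removes them and gives the small sample as the reason.

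**The concern.** The trial is meant to guide how far the rate can safely be raised. That calls for safety results arranged by rate, and the reason Table B gives for pooling does not bear on duration. A by-duration table pooled over cohorts would have larger cells than the SAP's own chart, which is split by both cohort and duration.

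As the SAP text stands, no planned summary shows how many infusions were given at each duration and how many of them had an IAR. Nor does any show whether AEs or post-infusion vital signs shift as infusions get faster. Visit does not stand in for duration: starting durations differ between participants (SAP 15.2.1.2 provides for starts below 90 minutes), and an IAR alters the step-down. A statement such as all 14 achieved the target, or no IAR occurred, would then appear with neither an infusion denominator nor an interval.

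**Working it through.** **1. The plan's own figures.** Cohorts: 3 + 3 + 4 + 4 = 14, as stated. Infusions every 2 weeks from Week 0 to Week 16: 16/2 + 1 = 9, as stated. There is no power calculation to reproduce.

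**2. Planned outputs, by grouping and unit.**

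| Output | SAP section | By duration? | Unit |
|---|---|---|---|
| AE, IAR and anaphylaxis tables | 16.1.7, 16.1.8 | No, pooled | Participants and AE occurrences, not infusions |
| Vital signs | 16.4.5 | No, by visit | Measurements |
| Any-IAR and second-IAR indicators | 15.2.1.3 | Yes | Participant, yes/no |
| Stacked bar chart | 15.2.3 | Yes, within cohort | Participants, IARs cumulative |
| Responder listing | 15.2.3 | Yes, by flag | Individual participant |
| Compliance | 14.1, 14.2 | No | Summed dose; doses listed by visit |

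No row has infusions as its denominator.

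**3. What the participant-level results leave open.** Under SAP 15.1.1.1, when a duration is repeated, "the infusion duration will be considered tolerated if the last infusion with the duration is tolerated". So on the second-IAR indicator, a first IAR at a duration followed by a tolerated repeat counts as yes. The any-IAR indicator does not have this weakness. The chart counts cumulatively, so it cannot always place an IAR. Take a cohort of 4 with bars of 3 with none and 1 with one IAR, then 2 with none and 1 with one IAR at the next duration. Two histories fit: an IAR-free participant left and there was no new IAR, or the one-IAR participant left and there was one new IAR.

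**4. Exact intervals at this n.** For the Clopper-Pearson 95% interval, the lower limit for n/n is 0.025^(1/n) and the upper limit for 0/n is 1 − 0.025^(1/n).

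| Result | Formula | 95% interval |
|---|---|---|
| 14/14 | 0.025^(1/14) = 0.768 | 76.8–100% |
| 13/14 | beta quantiles | 66.1–99.8% |
| 0/14 | 1 − 0.768 | 0–23.2% |
| 0/10 | 1 − 0.025^(1/10) | 0–30.8% |
| 0/4 | 1 − 0.025^(1/4) | 0–60.2% |

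The 0/10 and 0/4 rows describe the fastest step if every participant has one infusion there without an IAR: 10 participants at 20 minutes (≥30 kg) and 4 at 30 minutes (<30 kg).

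**5. Why the unit matters.** As an illustration, assume no IAR and starts of 120 minutes (≥30 kg) or 90 minutes (<30 kg). The amendment rationale for Section 4.5 (Protocol 10.6) then has completion at Week 8 (5 infusions) or Week 6 (4 infusions), so 10 × 5 + 4 × 4 = 66 infusions. Zero IARs would give an upper limit of 1 − 0.025^(1/66) = 5.4% per infusion, against 23.2% per participant and 30.8% at the 20-minute step. The 5.4% treats infusions as independent and is too narrow if IARs cluster within participants. The ceiling of 14 × 9 = 126 infusions is not used here: IAR-free participants step down and stop at target, so 126 is unlikely when there are no IARs.

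**6. AE follow-up after the fastest infusion.** Treatment ends once the target duration is tolerated (Protocol 4.5), and SAP 16.1 closes the treatment-emergent period on the last-dose date. The target infusion therefore contributes its own day, against about 14 days for each earlier one. IARs are same-day by definition, so none is lost. Later AEs go to the post-treatment table and listing.

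**The case against.** The strongest reply is that the protocol never firmly promised by-duration AE or vital-sign tables. The sentence in Protocol 9.3.1 is qualified, and it points to 9.3.2–9.3.4, not to 9.3.5, which itself plans safety by visit and by counts. That stands: a reader might infer a breach of protocol here, and the documents do not support it.

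A reader might also infer that IARs are never shown by duration. That is wrong. The any-IAR indicator catches an earlier IAR whatever the last infusion shows, and the responder, AE and dose listings would largely settle the chart example by hand. Treatment stops at a second IAR, so at most 14 × 2 = 28 infusions can have one. What remains is that hand reconstruction from listings is not a planned summary, and it does not give AE or vital-sign results by duration.

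On intervals, the protocol named no method, so no exact intervals were planned and then withdrawn. The removal is declared, the study has no hypotheses, and a reader could compute intervals from the counts. All true, but small n is a reason to show the width. On exposure, the unseen output templates (SAP 8) may contain the table, so the claim is confined to the SAP text.

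Finally, only those who tolerate slower infusions reach faster ones, so by-duration rates may flatter the fast steps. That limits interpretation but does not remove the case for a labelled descriptive table.

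**Conclusion.** The point holds as a mismatch between objective and analysis, and it is worth correcting because the cost is low. Its parts differ in standing:

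- **By-duration safety summary and infusion denominator:** a gap against the safety objective and the design rationale, only partly filled by participant-level IAR results.
- **Exposure summary:** an undeclared departure from Protocol 9.3.5, as far as the SAP text shows.
- **Intervals:** a declared removal for a weak reason. Even a perfect 14/14 is compatible with a true proportion of 76.8%. An IAR-free fastest step is compatible with IAR risks up to 30.8% (10 participants) or 60.2% (4 participants), assuming full enrolment and one infusion each at target.

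A reader might infer that AEs following the fastest infusion go unreported. They do not: SAP 16.1.8 gives post-treatment AEs their own summary and listing. The narrower point is that those AEs are not linked to the fastest infusion. The 66-infusion figure is illustrative only; shorter starts or early discontinuation would lower it, and longer starts or repeated durations would raise it.

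**What to change.** (a) Add one descriptive table by planned infusion duration, pooled over cohorts, with participants <30 kg shown separately where their flow differs. Give participants and infusions exposed; infusions with an IAR at that duration; AEs from each infusion to the next Fabrazyme infusion (study or non-study) or 14 days, whichever comes first; and vital-sign change from before to after infusion. State beneath it that only participants who tolerated slower infusions reach faster ones and that premedication is added after an IAR, so faster infusions can look safer.

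(b) Restore the exposure summary (number of infusions and exposure duration), or declare and justify its removal in Table B.

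(c) Show Clopper-Pearson 95% intervals for the participant-level binary endpoints, labelled descriptive.

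**Cost:** two tables and one column. The protocol already records what is needed: infusion start and stop times (6.5), medication received during the study (6.9), vital signs around each infusion (8.4.1) and AEs to the last visit (8.5.1). The downside is small cells, with at most 4 participants <30 kg, and wide intervals.
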